3.2. Endpoints

3.2.1. Primary Outcome Measure

- The time from randomization until initial clinical resolution of Norovirus symptoms for at least 48 hours through 180 days.

Clinical resolution will be assessed from the daily diary by the subject and will be defined as:

- Cessation of vomiting and,
- No stools classified by the Bristol Stool Chart as diarrhea (Type 6 or 7)

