3.3. Study Definitions and Derived Variables

Diarrhea:

Diarrhea will be defined as Type 6 or 7 on the Bristol Stool chart.

Baseline Value:

The baseline value will be defined as the last value obtained prior to the first dose of study product unless otherwise noted.

Additional Nitazoxanide:

Any nitazoxanide reported as a concomitant medication will be considered additional nitazoxanide.

Initial Clinical Resolution of Norovirus Symptoms:

Clinical resolution of Norovirus symptoms will be assessed from the daily diary by the subject and will be defined as:

- Cessation of vomiting and,
- No stools classified by the Bristol Stool Chart as diarrhea (Type 6 or 7).

Subjects will need to have at least two consecutive daily diary entries where they reported no vomiting, no Bristol Stool Type 6, and no Bristol Stool Type 7 to meet the criteria for initial clinical resolution. There are several variables in the daily diary that indicate whether the subject had diarrhea or vomiting for that day.

Daily Diary Diarrhea Questions:

- Phase 1 (Treatment Phase):
 - Number of Bristol Type 6 stools? (Quantitative)
 - Were there too many Bristol Type 6 stools to count? (Qualitative)
 - Number of Bristol Type 7 stools? (Quantitative)
 - Were there too many Bristol Type 7 stools to count? (Qualitative)
- Phase 2 (Longitudinal Phase):
 - Did you have diarrhea today? (By diarrhea, we mean at least ONE bowel movement that could be described as Type 6 or 7.) (Qualitative)

Daily Diary Vomiting Questions:

- Phase 1 (Treatment Phase):
 - Did you have to take another dose because you threw up the first dose within 1 hour? (Qualitative)
 - How many times did you vomit today? (Quantitative)
- Phase 2 (Longitudinal Phase):
 - Did you vomit today? (Qualitative)

For a day to count towards clinical resolution during the treatment phase, the following responses must be recorded in the daily diary entry:

- Both quantitative diarrhea questions must be 0

- Both qualitative diarrhea questions must be missing (i.e. not “yes”)
- The quantitative vomiting questions must be 0
- The qualitative vomiting question must be “no”

For a day to count towards clinical resolution during the longitudinal phase, the following responses must be recorded in the daily diary entry:

- The qualitative diarrhea question must be “no”
- The quantitative vomiting question must be 0

If a daily diary entry is missing, refer to the imputation rules in Section [6.5](#).

Viral Load:

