4.5.1. Efficacy Variables

The primary efficacy variables to be assessed are the cessation of vomiting and no stools classified by the Bristol Stool Chart as diarrhea (Type 6 or 7) and are based on outcomes reported in the Subject Daily Diary. The subject diaries were prepared by Northwestern University. They will be reviewed and collected at every visit, including unscheduled or early termination visits. The Subject Daily Symptom Dairies will be completed by the subject daily, in real-time, from Day 1 through Day 180. All diaries should be completed at the same time every day, when possible. Subjects will complete the NNITS Daily Symptom Diary [Day 1 – 28] from the time of study treatment dispensation until visit 05. At visit 05 (Study Day 28), subjects will complete the NNITS Daily Symptom Diary – Post Treatment [Day 29 – 180].

The exploratory efficacy variables for the following outcome measures are also based on subject daily diaries:

- Time from randomization to initial clinical improvement in Norovirus disease through 28 and 180 days for at least 48 hours.
- Time from randomization to initial cessation of vomiting through Day 180 (recurrent vomiting will be considered disease recurrence unless determined to be due to another etiology [i.e. GVHD]).
- Time from randomization to subject report of no loss of appetite that is maintained for 48 hours through Day 180 (measure will be first time that the subject reports that they have no “loss of appetite” on their daily diary).
- Time from randomization to initial cessation of diarrhea through Day 180 classified by the Bristol Stool Chart as type 6 or 7 bowel movements (recurrent diarrhea will be considered disease recurrence unless determined to be due to another etiology [i.e. GVHD]).
- Time from randomization to 50% reduction in the amount of antimotility agents utilized by the subject through Day 180.
- Number of days of diarrhea through Days 28 and 180.
- Number of stools classified by the Bristol Stool Chart as type 6 or 7 bowel movements through Day 28.
- Number of days of IV hydration or total parenteral nutrition (TPN) therapy through Day 28.

The secondary efficacy variable to be assessed is viral load and is based on stool for Norovirus assays. Norovirus viral load assays will be performed in the [name] Laboratory (CCHMC, Cincinnati, OH) and will be measured using Quantitative RT-PCR (qRT-PCR) at Study Days 1, 7, 14, 21, 28, 60, 120, 180, and with recurrent diarrhea.

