14.1.3. Daily Diary Completion Time

Subjects were instructed to complete their daily diary at the same time each day. During manual review of the data, it was discovered that subjects had entry dates with morning diary times and/or diary times that were <12 hours from their previous entry's diary time. Given the inconsistencies in the timing of the daily diary entries, it is difficult to know if subjects were recording information for the previous study day or the prior 24 hours. For diary entries that are <12 hours apart, it is likely that information has been duplicated. The analyses assume that the data reflected in each diary is for the date of diary completion; however, this is a limitation that was not able to be resolved during the study. The number of diaries completed in pre-specified windows (12pm – 6am, 6pm – 12am, 12am – 6am, and number completed less than 12 hours after previous diary completed) is provided in Listing 10.

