16.2.6 Individual Efficacy and Immunogenicity Response Data

Listing 12: 16.2.6.1: Individual Treatment Phase Daily Diary Data

[Implementation Note: “Too many” will be listed if number of stools was too many to count. If data is missing, it will be denoted as “—”. Rows will not be included for missing diary days. Imputation rules will not be included in the listings. Listing should be sorted by Treatment Group, Subject ID, Planned Time Point.]

Treatment Group	Subject ID	Transplant Type	Duration of Symptoms	Actual Study Day	Number of Bristol Type 6 Stools	Number of Bristol Type 7 Stools	Repeat Dose due to Vomiting	Number of Episodes of Vomiting
					[e.g. 7, Too Many]	[e.g. 7, Too Many]	Yes/No	

Listing 13: 16.2.6.2: Individual Longitudinal Phase Daily Diary Data

[Implementation Note: If data is missing, it will be denoted as “—”. Rows will not be included for missing diary days. Imputation rules will not be included in the listings. Listing should be sorted by Treatment Group, Subject ID, Planned Time Point.]

Treatment Group	Subject ID	Transplant Type	Duration of Symptoms	Actual Study Day	Diarrhea (At Least 1 Type 6 or 7 Bowel Movement)	Vomiting
					Yes/No	Yes/No

Listing 14: 16.2.6.3: Weekly Recall Diary

[Implementation Note: If data is missing, it will be denoted as “—”. Rows will not be included for missing weeks.]

Treatment Group	Subject ID	Transplant Type	Duration of Symptoms	Week Number ^a	Actual Study Day	Average Number Bowel Movements/Day	Average Number Vomiting Episodes/Day	% Type 6 or 7 Stool	% Type 3, 4, or 5 Stool	Abdominal Pain ^b	Urgency to Have Bowel Movement ^b	Fecal Incontinence ^b	Nausea ^b

^a Week Number is based off of Planned Time Point.

^b Subjects rated these symptoms as 0 being none and 10 being the worst possible.

Listing 15: 16.2.6.3: Individual PROMIS Scores Data – Quality of Life/PANAS

[Implementation Note: Listing will provide the PROMIS T-scores for IBSQOL. EurQOL Measures will be reported as ‘Problems’ or ‘No Problems’. Positive Affect and Negative Affect will be the reported scores based off of the Definitions in Section 3.3.]

Treatment Group	Subject ID	Transplant Type	Duration of Symptoms	Planned Time Point	Actual Study Day	Quality of Life (IBSQOL)	EuroQOL-5 Mobility	EuroQOL-5 Self-Care	EuroQOL-5 Usual Activities	EuroQOL-5 Pain/Discomfort	EuroQOL-5 Anxiety/Depression	EuroQOL-5 Health State	Positive Affect	Negative Affect	EuroQOL-5 Mobility

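### SAP 3.3 diary rules: a Day 1 antidiarrheal count of zero is scored as an immediate event, likely duplicated entries in the primary endpoint go untested, and one vomiting line needs an editorial correction

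*SAP*

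**What the plan says.** **Antimotility outcome (exploratory).** SAP 3.3 takes the daily antidiarrheal count from the Phase 1 (Treatment Phase) diary. The event is placed on the first study day whose count is no more than half the Day 1 count. Protocol 3.2.3 (item 5) and SAP 3.2.4 both run this outcome from randomization to Day 180.

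**Primary endpoint.** SAP 3.2.1 asks for "initial clinical resolution of Norovirus symptoms for at least 48 hours through 180 days". SAP 3.3 implements this as follows: "Subjects will need to have at least two consecutive daily diary entries where they reported no vomiting, no Bristol Stool Type 6", and no Type 7 either. It sets no minimum time between the two entries. SAP 4.5.1 gives the expectation: "All diaries should be completed at the same time every day, when possible". SAP 14.1.3 then reports that some entries carried morning times and that some came less than 12 hours after the one before. It states "For diary entries that are <12 hours apart, it is likely that information has been duplicated" and that "it is difficult to know if subjects were recording information for the previous study day or the prior 24 hours". Its working assumption is that each entry describes the date on which it was completed, and it accepts that the problem was left unresolved. Listing 10, whose title limits it to the Treatment Phase, gives per-subject counts.

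**Day 29-180 vomiting line.** For a Longitudinal Phase day to count, SAP 3.3 says "The quantitative vomiting question must be 0". The one Phase 2 vomiting item in the same section is "Did you vomit today? (Qualitative", a yes/no question. Listing 13, "Individual Longitudinal Phase Daily Diary Data", shows the vomiting column as Yes/No.

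**The concern.** The antimotility rule gives a wrong answer when it is followed exactly. A subject taking no antidiarrheals on Day 1 has nothing to reduce, but is scored as the earliest possible success. The outcome is also reported under a Day 180 label while its derivation stops drawing data at Day 28.

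The spacing question touches the primary endpoint. The endpoint is *initial* resolution, and SAP 6.5 ignores missing data after resolution, so one accepted pair of clean entries fixes the event. If the second entry repeats the first, less than 48 hours of symptom-free report can be scored as the event. Within a subject, accepting such a pair can only bring the event forward or turn a censored time into an event. Nothing planned would show whether the hazard ratio depends on these pairs.

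The vomiting line matters only because the SAP text and the analysis program should agree.

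**Working it through.** The plan gives no figure for any of these points (Listing 10 is an empty shell), so there is none to reproduce.

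**1. Antimotility rule.** Let *c1* be the Day 1 count and *ct* the count on day *t*. The event is the first *t* with *ct* ≤ 0.5 × *c1*.
- If *c1* = 4, the threshold is 2. Day 1 itself fails (4 > 2), and a real reduction is needed.
- If *c1* = 0, the threshold is 0 and Day 1 already passes (0 ≤ 0).
- The eligibility criteria in SAP 4.3 do not require antimotility use, so zero counts are plausible. Their number is not given.
- Days 29-180 make up 180 − 28 = 152 of 180 days, and the derivation has no antidiarrheal count for any of them. SAP 14.2 does not record this departure.

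**2. What two close entries cover.** Take entries at clock hour *a* on one date and *b* on the next. The gap is *g* = 24 − *a* + *b*.
- If each entry recalls the prior 24 hours, coverage is 24 + *g* for *g* ≤ 24. So *g* < 12 gives less than 36 h, and *g* = 24 gives 48 h.
- If each entry covers midnight to completion, coverage is *a* + *b*. Since *b* = *g* − (24 − *a*) ≤ *g* and *a* ≤ 24, *a* + *b* ≤ 24 + *g*, again less than 36 h.
- Example, 22:00 then 08:00: *g* = 24 − 22 + 8 = 10. Coverage is 24 + 10 = 34 h under the first reading and 22 + 8 = 30 h under the second.
- If the evening entry describes its own date and the morning entry the previous study day, both describe the same day and the pair covers at most 24 h.

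**3. Planned analyses against this problem.**
- SAP 6.5 and 8.1.1, worst case: subjects who drop out or stop their diaries.
- SAP 6.4 and 8.1.1, subgroups: additional nitazoxanide and chromaturia.
- SAP 8.1.1, diary compliance: fewer than 2 versus 2 or more *missing* diaries per week.
- SAP 6.3.2, per-protocol population: diary compliance judged by missing days only, so a duplicated entry counts as compliant.

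None of these depends on the time between entries.

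**4. What a 12-hour filter would and would not do.**
- Under midnight-to-completion recall, an 08:00/08:00 pair covers 8 + 8 = 16 h and would be kept, while the 22:00/08:00 pair covers 30 h and would be dropped.
- Under prior-24-hour recall, gaps of 12 to 23 h cover 36 to 47 h and would also be kept.

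The filter therefore tests duplication only.

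**5. Vomiting line.** SAP 3.3 says in words that the subject must have reported no vomiting, offers one Phase 2 vomiting item, and Listing 13 shows that item as Yes/No. Only one reading is possible.

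**The case against.** Much of the opposing case stands. The vomiting line is a clerical slip. A reader might infer that, taken literally, no subject could resolve after Day 28. The documents do not support that, because the governing sentence and the listing both show what is meant.

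On spacing, the SAP discloses the problem, states an assumption and lists counts. Under that assumption two consecutive entries are two calendar dates, and the short coverage figures arise only if the assumption fails. A reader might go further and infer that the primary hazard ratio is biased. Nothing supports that: the number of close pairs is not given, the trial is blinded, and no reason appears for the arms to differ. SAP 14.2 says 31 subjects enrolled and that analyses will be mainly descriptive, so the value of another analysis is modest. A reader might also take a 12-hour filter as enforcing 48 hours. Step 4 shows that it does not, and it leaves open the recall question raised by the morning entries.

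What remains is that disclosure and a listing do not show whether the result depends on entries that the SAP itself calls likely duplicates.

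On the antimotility outcome, SAP 8.3 allows comparison through Day 28 and/or Day 180 for this group of outcomes, which partly accommodates a Day 28 horizon. It does not assign Day 28 to this outcome, and it does nothing about zero counts. The outcome is one of many exploratory ones, and the number of subjects with a Day 1 count of 0 could be none.

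**Conclusion.** The point holds at three different weights.

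- **Antimotility rule:** wrong as written, but exploratory. Followed exactly, it scores every Day 1 count of 0 as an immediate event, and it draws on 28 of the 180 days that the outcome names. How many subjects this affects is unknown.
- **Entry spacing:** a cheap improvement to the reporting of the primary endpoint. A pair under 12 hours apart covers less than 36 h under prior-24-hour or midnight-to-completion recall, and at most 24 h if both entries describe one day. These figures assume that SAP 14.1.3's completion-date assumption fails for the pair. The number of pairs and the effect on the hazard ratio are unknown.
- **Vomiting line:** editorial only, with no effect on any result.

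**What to change.** **SAP 3.3 and 14.2, antimotility.** Restrict the outcome to subjects with a Day 1 count above 0, report it through Day 28 (Table 29, Figure 24), and record the departure from the protocol's Day 180 outcome in SAP 14.2. The cost is a smaller denominator.

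**SAP 8.1.1, spacing.** Add one descriptive sensitivity analysis of the primary endpoint in the mITT population. A symptom-free entry completed less than 12 hours after the previous one cannot supply the second clean day, and its date is not filled back in as symptom-free under SAP 6.5. A symptomatic entry still breaks the run. Present this as a check on duplicated entries only, not as enforcing 48 hours or settling what morning entries describe. State whether completion times are held for Days 29-180. If they are not, say that the check applies to the Treatment Phase only, so that the rule is stricter before Day 29 than after it. No new data are needed, and the primary analysis is unchanged.

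**SAP 3.3, vomiting.** Replace the Day 29-180 vomiting condition with the Phase 2 yes/no item answered no. This is one line.

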3.2.2 Secondary Outcome Measures

Virologic Efficacy

1. Time from randomization to first negative viral load through 180 days.
2. The change in viral titer between Day 1 and 180.

Safety

3. Incidence of unsolicited non-serious adverse events (see section 9 for details) through 60 days.
4. Incidence of laboratory adverse events (WBC, Hemoglobin, Platelet Count, Creatinine, Alkaline Phosphatase, ALT, AST, BUN and Bilirubin) through 60 days.
5. Incidence of protocol-specified serious adverse events (see section 9 for details) through 60 days.
6. Incidence of Hospitalization through 60 days.

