8.2.2 Special Assays or Procedures

1. Stool for Norovirus Assays: These assays will be performed in the [name] Laboratory (CCHMC, Cincinnati, OH). Bulk stool samples are collected from subjects and aliquoted on site into cryovials. Aliquots are frozen at $<-70^{\circ}\text{C}$ before shipment to the [name] Lab. One-gram bulk stool aliquots are necessary for the following assays.
 - a. Norovirus Quantitative RT-PCR (qRT-PCR): Stool suspensions (10% w/v) will be prepared in sterile water. Viral RNA will be purified from the clarified extracts using the QiaAmp Viral Mini kit (Qiagen) according to the manufacturer's instructions. The viral RNA will be eluted in a final volume of 60ul. Each sample will be tested in triplicate using the TaqMan Fast Virus 1-Step Master Mix (Applied Biosystems). GI NoVs are amplified with forward primer – QNIF4 5'CGC TGG ATG CGN TTC CAT, reverse primer – NV1LCR 5'CCT TAG ACG CCA TCA TTT AC, and probe – NV1LCpr 5'VIC-TGG ACA GGA GAY CGC RAT CT-MGBNFQ, while GII NoVs are amplified with forward primer – QNIF2d 5'ATG TTC AGR TGG ATG AGR TTC TCW GA, reverse primer – Cog2R 5'TCG ACG CCA TCT TCA TTC ACA, and probe – RING2 5'6-FAM-TGG GAG GGC GAT CGC AAT CT-MGBNFQ. Real-time RT-PCR will be performed using the 7500 Fast Real-time PCR System (Applied Biosystems). All samples will be compared among each other, as well as against known GI and GII positive controls for relative Ct values.

Stool samples will be processed for extraction of norovirus RNAs. RT-PCR will be performed via a standard procedure using primers targeting the RNA-dependent RNA polymerase gene of norovirus genome. This will result in a 319-nucleotide fragment as PCR products. PCRs will contain 40 cycles of amplifications; a positive and negative control will be included to make sure PCR being working. As explained above, stool sampling will be performed according to an SOP; there is no approaches at the laboratory level to account for sampling error. The PCR product of norovirus genome fragment will be sequenced at CCHMC's DNA Sequencing Core Facility equipped with state-of-the-art capillary DNA analyzers (Sanger Sequencing).

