As Norovirus surveillance laboratories have observed that Norovirus type GII is predominant compared to Norovirus type GI and dual infection by both GI and GII viruses is rare, all specimens are tested for Norovirus GII viral load first ([name], [name], person communication). Only specimens that are negative for Norovirus GII viral load will be tested for Norovirus GI viral load. Subjects will only be analyzed for the viral load test type (Norovirus GII or Norovirus GI) that they tested positive for at baseline (Visit 01). If a subject initially tested positive for GI and later tested positive for Norovirus GII before they tested negative for Norovirus GI, the subject will be considered positive for Norovirus GI until they test negative for Norovirus GII and Norovirus GI. Subjects that did not test positive for either Norovirus GII or Norovirus GI at baseline will be excluded from the analyses. The first day of undetectable quantitative Norovirus PCR is the first day the subject had either a negative result or a result less than the lower limit of quantitation (LLOQ) for the viral load test type (Norovirus GII or Norovirus GI) that they initially tested positive for at baseline. Viral load will be quantified as the geometric mean of the replicates. Negative results will be imputed as $\frac{1}{2}$ the LLOQ and results greater than the upper limit of quantification (ULOQ) will be imputed as the ULOQ.

Initial Clinical Improvement in Norovirus Disease:

Initial clinical improvement in Norovirus disease through 28 and 180 days for at least 48 hours, is defined by:

- a. 50% reduction in number of episodes of vomiting and,
- b. Improvement in PO intake, as judged by the subjects and,
- c. 50% reduction in the number of episodes of diarrhea as classified by the subject by the Bristol Stool Chart as type 6 or 7 bowel movements.

The baseline values for number of episodes of vomiting and diarrhea will be the numbers provided on the first non-missing daily diary entry for the vomiting and diarrhea questions, respectively. Subjects must answer “yes” to the daily diary question “Did you eat your usual diet today?” to meet the improvement in PO intake criteria.

Detailed Patient-Reported Outcome (PRO) Measures:

Study personnel will administer detailed PRO questionnaires to subjects at Visit 01 (Day 1), Visit 05 (Day 28), Visit 08 (Day 60), Visit 10 (Day 120), and Visit 12 (Day 180).

Quality of Life.

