8.2. Secondary Efficacy Analyses

The secondary efficacy outcome measures are as follows:

- The time from randomization to first negative viral load through 180 days.
- The change in viral titer between Day 1 and Day 180.

The protocol calls for a Log-Rank test to compare time from randomization to first negative viral load through 180 days between the nitazoxanide treated group and the placebo group; however, due to early closure of the study, the number of subjects is too small to use a Log-Rank test. Number and percentage of subjects with positive viral load and geometric mean viral titer in positive subjects with 95% confidence intervals will be presented by test type, treatment group and study day in the mITT Population ([Table 20](#)). A stratified Cox proportional hazards model will be used to compare treatment to control through Day 180 with respect to time to first negative viral load. Stratification will be based on acute versus chronic symptoms at baseline. GII and GI test types will be analyzed independently.

The analysis will be conducted in both the mITT population and the PP population. The treatment hazard ratio estimate, 95% confidence interval and p-value from the likelihood ratio test will be presented for each test type ([Table 21](#) and [Table 22](#)). The median time to clinical resolution and 95% confidence interval will be summarized by treatment arm and duration of symptoms for each test type. In addition, stratum-specific estimates of the treatment hazard ratio within each duration of symptoms strata will be presented for each test type. Kaplan-Meier curves for each treatment arm will be displayed in [Figure 10](#), [Figure 11](#), [Figure 12](#) and [Figure 13](#), for each test type in the mITT and PP populations. [Figure 14](#) and [Figure 15](#) will present Kaplan-Meier curves for each treatment arm and duration of symptoms strata for Norovirus GII and Norovirus GI test types, respectively, in the mITT population.

The analysis will be repeated on the mITT population using the subgroups defined in Section [6.4](#) for each test type ([Table 23](#) and [Table 24](#)).

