N = Number of subjects in the specified treatment group, duration of symptoms strata, and analysis population with positive Norovirus GII test results at baseline.

n = Number of subjects with first negative Norovirus GII viral load test result.

Note: HR is the ratio of the hazard of first negative Norovirus GII viral load in each treatment group estimated from the Cox model. The ratio is Nitazoxanide 500 mg to Placebo.

HR for the ‘Any Duration’ group is the hazard ratio from the stratified Cox Model.

P-value calculated using the likelihood ratio test.

Table with similar format:

Table 22: Time to First Negative Viral Load by Treatment Group and Duration of Symptoms – Norovirus GI

Table 23: Time to First Negative Viral Load by Treatment Group and Duration of Symptoms: Subgroup Sensitivity Analysis – Norovirus GII, mITT Population

Implementation Note: If an estimate is not calculable, insert “NC” in the cell and add a footnote “NC = Not calculable.” If a subgroup has less than 5 subjects per treatment group, then remove rows and add footnote specifying which group(s) are excluded from analyses.

Subgroup	Treatment Group	Duration of Symptoms	n	Median Time to First Negative Viral Load		HR		P-value
				Estimate	95% CI	Estimate	95% CI	
Additional Nitazoxanide 500 mg ^a	Nitazoxanide 500 mg (N=X)	Acute	x	x.x	x.x, x.x	x.xx	x.xx, x.xx	--
	Placebo (N=X)		x	x.x	x.x, x.x			
	Nitazoxanide 500 mg (N=X)	Chronic	x	x.x	x.x, x.x	x.xx	x.xx, x.xx	--
	Placebo (N=X)		x	x.x	x.x, x.x			
	Nitazoxanide 500 mg (N=X)	Any Duration	x	x.x	x.x, x.x	x.xx	x.xx, x.xx	0.xxx
	Placebo (N=X)		x	x.x	x.x, x.x			
Chromaturia ^b	Nitazoxanide 500 mg (N=X)	Acute	x	x.x	x.x, x.x	x.xx	x.xx, x.xx	--
	Placebo (N=X)		x	x.x	x.x, x.x			
	Nitazoxanide 500 mg (N=X)	Chronic	x	x.x	x.x, x.x	x.xx	x.xx, x.xx	--
	Placebo (N=X)		x	x.x	x.x, x.x			
	Nitazoxanide 500 mg (N=X)	Any Duration	x	x.x	x.x, x.x	x.xx	x.xx, x.xx	0.xxx
	Placebo (N=X)		x	x.x	x.x, x.x			

N = Number of subjects in the specified treatment group, subgroup, and duration of symptoms strata with positive GII test results at baseline.

n = Number of subjects with first negative GII viral load test result.

^a Subjects that took additional Nitazoxanide 500 mg are excluded from the analyses.

^b Subjects with unsolicited self-reported chromaturia (discoloration of urine) are excluded from the analyses.

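### SAP 3.3 scores only negative PCR results at half the LLOQ, so a detected result below half the LLOQ can score lower than a true negative, and 'negative viral load' is never defined

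*SAP*

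**What the plan says.** **Endpoint.** The first virologic secondary outcome (Protocol 3.2.2, repeated in SAP 3.2.2) is "Time from randomization to first negative viral load through 180 days". SAP 8.2 fits a stratified Cox model to "compare treatment to control through Day 180 with respect to time to first negative viral load". Neither says what counts as negative. The footnote to SAP Table 21 only repeats the word: "n = Number of subjects with first negative Norovirus GII viral load test result".

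**Undetectable rule.** SAP 3.3, under Viral Load, defines the first day of undetectable PCR as "the first day the subject had either a negative result or a result less than the lower limit of quantitation (LLOQ") for the genogroup that was positive at baseline. SAP 10 refers to this definition by section number for the correlations in Tables 46-47. The shells for those tables head the same variable as the first day with a negative PCR.

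**Titer rule.** Also in SAP 3.3:
- "Viral load will be quantified as the geometric mean of the replicates". Protocol 8.2.2 adds: "Each sample will be tested in triplicate".
- At the low end, "Negative results will be imputed as" half the LLOQ.
- At the high end, "results greater than the upper limit of quantification (ULOQ) will be imputed as the ULOQ".

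**Baseline.** SAP 3.3 restricts the viral-load analyses to subjects positive for GII or GI at Visit 01. It does not say whether a result detected below the LLOQ is positive.

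**The concern.** The high-end titer rule is tied to an assay limit, but the low-end rule is tied to a result label. The same definition has just treated that label as something other than below-LLOQ. A detected result below the LLOQ therefore falls between the two rules.

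Two things are at stake:
- **Titer.** The ANCOVA of change from Day 1 to Day 180 (Tables 25-28) can rank a subject still shedding at a low level as better than one who has cleared.
- **Event date.** With 'negative' undefined, two programmers could follow the SAP and reach different clearance dates in Tables 21-24 and 35-36. Those dates could also differ from the dates in Tables 46-47, where the same label is used.

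**Working it through.** The plan states no figure for this point, so there is none to reproduce. The check sets the rules side by side and then does log10 arithmetic in multiples of the LLOQ.

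**1. What each rule does with each result (SAP 3.3)**

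| Result | Undetectable? | Titer value |
|---|---|---|
| Negative | Yes | 0.5 x LLOQ |
| Detected, below LLOQ | Yes | No rule |
| LLOQ to ULOQ | No | Measured value |
| Above ULOQ | No | ULOQ |

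No other section fills the second row. SAP 6.5 confines imputation for missing data to diary entries for the primary endpoint. The immunoglobulin rule in SAP 3.3 is tied to the assay's lower limit and so has no such gap.

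**2. Score of a detected result left at its raw value, relative to a negative**

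Let r be the result divided by the LLOQ. A negative scores log10(0.5) = -0.301 relative to log10 LLOQ. The difference is d = log10(r) - log10(0.5).

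| r | log10(r) | d |
|---|---|---|
| 0.99 | -0.004 | +0.297 |
| 0.5 | -0.301 | 0 |
| 0.25 | -0.602 | -0.301 |
| 0.1 | -1.000 | -0.699 |
| 0.01 | -2.000 | -1.699 |

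Below r = 0.5 the order reverses: the detected sample scores lower than the negative one.

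**3. Effect on an arm mean (illustration)**

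The shift in the mean log10 titer at one visit is (k/n) x d, where k of n subjects have such a result. SAP 6.6 gives 31 enrolled, so n = 15 per arm is assumed. The value k = 3 is also an assumption.
- r close to 1: (3/15) x 0.301 = +0.06
- r = 0.1: (3/15) x (-0.699) = -0.14
- r = 0.01: (3/15) x (-1.699) = -0.34

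With n = 10 the same three cases give +0.09, -0.21 and -0.51. The analysis is split by genogroup and needs a Day 180 sample, so the true n may be smaller. The difference between arms moves only as far as the arms differ in how many such samples they have.

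**4. Replicates**

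A negative replicate has no logarithm until it is given a value. A mixed triplicate therefore has a geometric mean only if the half-LLOQ value is put in first or the negative replicate is left out. SAP 3.3 does not say which.

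**5. Readings of 'negative'**

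- *Strict throughout:* the two secondary endpoints use the same category, but detected results below the LLOQ still lack a titer rule. Tables 46-47 can date clearance earlier than Tables 21-24 and 35-36.
- *Broad throughout (below-LLOQ included):* all the rules agree. This makes the word include a category that the same definition lists as its alternative.
- *Broad for the event, strict for titer:* the same sample is cleared in one secondary endpoint and has no assigned titer in the other.

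**6. Baseline**

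If a Day 1 result detected below the LLOQ counts as positive, it admits the subject to the analysis and meets the undetectable rule on the same day.

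**The case against.** The strongest reply is that the documents contain no outright contradiction. The undetectable rule is expressly used only for the exploratory correlations in SAP 10. SAP 8.2 does not point to it, and the strict and broad readings each make the two secondary endpoints agree. That stands. A reader might infer that the SAP clears a sample in one secondary endpoint and leaves it raw in the other. That needs the third reading in the working, which the text does not state. Likewise, a raw or missing titer follows from the plan's silence and is not a stated rule.

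Three further inferences are not supported:
- **A shift of so many days in clearance time.** The documents give no LLOQ, detection limit or rate of viral decline. Scheduled samples fall only on Days 1, 7, 14, 21, 28, 60, 120 and 180, so any shift would be from one sampling day to another.
- **Clearance generally scored as a rise in titer.** The ANCOVA uses only Day 1 and Day 180. A spurious rise needs a Day 1 result below half the LLOQ that still counts as positive. Subjects enrol with active symptoms and a recent positive test, and Protocol 2.1 puts stool titers generally at 10^5 to 10^10 copies per gram.
- **Different handling of GI and GII as an error.** GI is tested only when GII is negative, so a GI-baseline subject who is GII-positive has no GI result. The special rule covers that case.

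Whether the event should be strict negativity or below-LLOQ is a genuine trade-off. The strict reading stays closer to the protocol's wording.

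What survives is the titer gap, the undefined event term, and their overlap at baseline.

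**Conclusion.** The concern holds in this limited form. SAP 3.3 separates negative from below-LLOQ, calls both undetectable, and gives a titer value to only one of them. Applied literally, a detected result under half the LLOQ scores below a true negative: by 0.30 log10 at 0.25 x LLOQ and 0.70 at 0.1 x LLOQ. If the laboratory reports no number, the sample drops out of the titer analysis.

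These sizes assume that raw values are reported and that titer is analysed on the log scale, which SAP 8.2 leaves open. On the raw copy scale the inversion is always less than half an LLOQ. The number of such samples is unknown and may be zero.

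First negative viral load needs a definition under any reading, because the variable called undetectable in SAP 10 appears under a negative heading in Tables 46-47. The primary endpoint, sample size and alpha are unaffected, and SAP 14.2 expects the analyses to be mainly descriptive. The change is still worth making, because both secondary efficacy endpoints depend on this definition.

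**What to change.** 1. In SAP 3.3, extend the half-LLOQ rule to cover negative results and all results below the LLOQ. Every such sample then scores log10(LLOQ) - 0.301 and the inversion disappears.
2. State whether this is done for each replicate before the geometric mean or for the sample afterwards.
3. State once whether negative viral load includes results below the LLOQ. Use that category for the event in Tables 21-24 and 35-36, for positivity at baseline and for Table 20. Align the heading of Tables 46-47 with the variable they use.
4. Report the other definition of the event as a sensitivity analysis.

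The cost is a few sentences of SAP text and one repeat of the time-to-negative tables. If results below the LLOQ are not positive, a subject below the LLOQ on Day 1 leaves the viral-load set. The choice should be made before results by treatment group are seen. If that is no longer possible, it should be recorded and justified in the clinical study report, as the SAP Preface provides for deviations.
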